### **j) Withdrawal of Subjects**

If they choose to consent to the study and are eligible to begin the trial, they will be closely monitored and will visit with the study coordinator and study physician. Side effects will be rated weekly at each visit using an adverse events checklist completed by a study physician. Subjects with an exacerbation of psychosis/depression/mania on a 2-point CGI-change score will be discontinued and treated appropriately by the study physician. Suicidal ideation will be assessed at each visit with the Beck (SSI) and the Columbia Suicide Severity Rating Scale (C-SSRS). Significant suicidal ideation will be addressed immediately using the standard clinical response at ISMMS (evaluation at the walk-in clinic/psychiatric emergency room for potential need to hospitalize). Subjects at risk for suicidal behavior will be discontinued. Subjects with any other clinical worsening as noted by study physician, and any instance of an SAE will be discontinued. In addition, subjects who exhibit any inability to follow the protocol will be discontinued and withdrawn from the study.

To ensure orderly termination from the study, the study physician would meet with the subject to discuss termination and discontinuation of medication. Safety measures would be collected and a follow-up visit by phone would be scheduled to further ensure safe discontinuation. Discontinuing isradipine does not require a taper. We will schedule an in-person visit if necessary after the follow-up visit by phone to address any remaining concerns the subject may have.

Subjects may withdraw from the study for any reason at any time by contacting the principal investigator or any of the research staff. It is also possible to withdraw permission for the use and disclosure of any protected information for research, but it must be done in writing to the principal investigator. In the event permission is withdrawn, information that was already collected may still be used if that information is necessary to complete the research study.

### **6) Risks to Subjects**

During the informed consent process, subjects will be informed of the potential risks associated with the study. Isradipine has not been shown to induce or worsen psychosis in any of the published human data; nonetheless, symptoms may worsen in the course of the study. We will very closely monitor psychotic and affective symptoms on a weekly basis

	Protocol Title:	A Molecular Approach to Treat Cognition in Schizophrenia: Ca 2+ Channel Blockade
	Principal Investigator Name/Contact Info:	[name] [contact]
	Primary Contact Name/Contact Info:	[name] [REDACTED]
	Date Revised:	May 16, 2017
	Study Number:	HSM# 12-0031, GCO# 12-0679, GCO# 13-1987

throughout the study period using standardized rating scales described above in 5f). At each weekly visit the study physician will meet with the patients and conduct a thorough review of symptoms including psychosis, mood, and suicidal/homicidal ideation. If there is an acute worsening of symptoms the study clinicians will review the case with the PI (or will make an emergency decision as needed) to ensure that the subject receives emergency care or hospitalization. Participation in the study will be discontinued in any case of clear symptom worsening. Between weekly visits, the patients will have emergency contact information.

Along with closely monitoring for symptom exacerbation, each visit with the study physician will entail a detailed side effect evaluation, which will include vital signs and a side effect checklist. The most common side effects of isradipine include hypotension, edema, headache, dizziness, palpitations, fatigue, flushing, and constipation. Patients will be educated about the potential for hypotension and its symptoms, and blood pressure and symptoms will be measured at every visit. If the patient develops clinically significant hypotension (e.g., systolic blood pressure equal to or less than 90 mm Hg or diastolic equal to or less than 60 mm Hg, or if they experience significant associated symptoms), or if at any point in the study subsequent to baseline there is a blood pressure drop of 20% or more from blood pressure at baseline, they will be discontinued from the study medication and excluded from the protocol. Rare side effects have also been reported including arrhythmias, syncope, severe hypotension or myocardial infarction. The informed consent process will alert subjects to these potential risks and close monitoring will ensure prompt response to any adverse effects with appropriate treatment and/or study discontinuation, as indicated.

Additional risks are minimal and involve the completion of questionnaires, interviews and paper-pencil/computerized tests. Some of the questions may be distressing to the individual and subjects will be told that they may refuse to answer any questions that they so choose. The testing procedure can sometimes cause fatigue but we will ensure plenty of resting periods during the session and will instruct subjects to notify staff if they would like an additional break. Pain and bruising may be associated with the blood draw for screening labs; however, a trained phlebotomist will perform the procedure to avoid any additional discomfort.

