### b) Inclusion and Exclusion Criteria

**Inclusion criteria:** **1.** Age 18-60; **2.** DSM-IV schizophrenia or schizoaffective diagnosis; **3.** Residual phase of illness criteria met at screen and baseline as defined by item scores of  $\leq 4$  on each of the Brief Psychiatric Rating Scale (BPRS) hallucinatory behavior, unusual thought content, and conceptual disorganization items; **4.** Hamilton Rating Scale for Depression (HRSD)  $\leq 12$ ; **5.** Baseline Clinician Administered Ratings Scale for Mania (CARS-M) score of  $< 5$ ; **6.** Simpson Angus Scale (SAS) total score of  $\leq 6$ ; **7.** Treatment with at least one but no more than two stably-dosed second-generation antipsychotic medication (other than clozapine) for  $\geq 2$  months and no changes planned over the 4-week study period. First generation antipsychotics and clozapine are thought to cause significant cognitive impairment. Initial baseline cognitive functioning will not be evaluated as inclusion/exclusion criterion because schizophrenia/schizoaffective disorder have a relatively cognitively homogeneous patient sample. We do not anticipate any subjects without cognitive impairment. We will cover for baseline performance to determine if degree of cognitive impairment at baseline is responsible for any change noted.

**Exclusion criteria:** **1.** History of CNS trauma, neurological disorder, ADHD, mental retardation, learning disability, or other non-schizophrenic cause of cognitive impairment; **2.** DSM-IV diagnosis of substance abuse/dependence within 3 months or positive urine toxicology at screening that is not consistent with what participant reported. Substance abuse and dependence are determined based on an extremely comprehensive interview (the SCID), which evaluates lifetime history and current history of all substance use disorders. As per the protocol, DSM-IV diagnosis of substance abuse or dependence within 3 months will be exclusionary (not substance use); **3.** Pregnant women or women of child bearing potential who are not using a medically accepted means of contraception (including oral contraceptive or implant, condom, diaphragm, spermicide, intrauterine device, tubal ligation, or partner with vasectomy) **4.** Women who are breastfeeding; **5.** Active, unstable medical problem that may interfere with cognition; **6.** Current treatment for hypertension; **7.** Uncontrolled hypertension; **8.** History of heart

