	Protocol Title:	A Molecular Approach to Treat Cognition in Schizophrenia: Ca 2+ Channel Blockade
	Principal Investigator Name/Contact Info:	[name] [contact]
	Primary Contact Name/Contact Info:	[name] [REDACTED]
	Date Revised:	May 16, 2017
	Study Number:	HSM# 12-0031, GCO# 12-0679, GCO# 13-1987

disease; **9.** Any drug known to interact with isradipine. **10.** History of GI strictures; **11.** Abnormal lab or ECG at screen. **12.** Significant suicidal ideation at baseline (HRSD item 3 > 2). Concomitant Medications: Practical and ethical considerations prevent an exclusive focus on medication-free patients; however, we will limit participation to individuals taking at least one and no more than 2 concomitant antipsychotic medications and we will exclude subjects who have received ECT within 12 months. Medication load will be incorporated as covariates in statistical analyses using chlorpromazine (CPZ) equivalents.

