### d) Study Timelines

The recruitment and enrollment process will be active for approximately 24 months. The anticipated final date for this study is 7/2017. The patients will be informed of the length of the study, which will include 8 visits in total. There will be a screening visit, baseline visit when they will receive the study medication, a visit eight hours after the first dose of medication is taken (baseline) where blood pressure will be checked, 4 weeks of medication administration and weekly monitoring, and a visit eight hours after the dosage of the medication is increased (week 2) where blood pressure will be checked. They will be informed of all of the study procedures for each week, including assessments and medical tests.

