### f) Procedures Involved in the Human Research

All eligible subjects will undergo visits at screening, baseline (week 0), visit 8 hours after week 0, week 1, week 2, visit 8 hours after week 2, week 3, and week 4 (end of study). The parameters of study drug dosing are as follows: isradipine as utilized in this trial will be administered twice daily. Isradipine will be titrated as follows: baseline (week 0) 5 mg/day BID; Week 2 increase to 10 mg/day BID if 5 mg was well-tolerated. Dosing will be flexible based on side effects with a maximum=10 mg/day. If 5 mg cannot be tolerated, the subject will be discontinued. Dosing was based on package labeling for hypertension and prior studies in Parkinson's disease (Simuni et al. 2010).

	Protocol Title:	A Molecular Approach to Treat Cognition in Schizophrenia: Ca 2+ Channel Blockade
	Principal Investigator Name/Contact Info:	[name] [contact]
	Primary Contact Name/Contact Info:	[name] [REDACTED]
	Date Revised:	May 16, 2017
	Study Number:	HSM# 12-0031, GCO# 12-0679, GCO# 13-1987

Measures described in detail below:

Safety Outcome Measures

- The Side Effects Checklist (SEC; physician administered) and side effect self-report form – (all visits)
- Vital signs including blood pressure (standing/supine – all visits)
- Blood pressure check within 8 hours of first dose. Staff contact number will be given to subject in case there are any problems before the 8 hour BP check (week 0). An additional blood pressure check 8 hours after increased dosage (week 2).
- Electrocardiogram (ECG); chemistry panel and CBC via blood draw (approximately 2 TSP blood drawn); urinalysis (screening & week 4)
- Urine toxicology (screening)
- Urine pregnancy test for women of childbearing potential (baseline)
- Abnormal Involuntary Movement Scale (AIMS) and Simpson Angus Scale (SAS) (all visits)
- Beck Scale for Suicidal Ideation (SSI) and Columbia Suicide Severity Rating Scale (C-SSRS) (all visits)

Clinical/Symptom Measures

- Structured Clinical Interview for the DSM-IV (SCID-IV) (screening)
- Symptom rating scales including the Brief Psychiatric Rating Scale (BPRS), the Scale for the Assessment of Negative Symptoms (SANS), the Hamilton Rating Scale for Depression (HRSD), the Clinical Global Impression Scale (CGI), the Clinician Administered Rating Scale for Mania (CARS-M) (all visits)

Neurocognitive/Functional Measures

- MATRICS Consensus Cognitive Battery\* (baseline & week 4)

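### No lower blood-pressure limit at entry: a patient already at the protocol's own example of hypotension can be given a first dose of isradipine

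*Combined protocol and SAP*

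**What the plan says.** Section 5b deals with blood pressure in two exclusions, both about high pressure: number 6, "Current treatment for hypertension", and number 7, "Uncontrolled hypertension". Two other exclusions might be thought to catch a low reading. Number 5 is worded as "Active, unstable medical problem that may interfere with cognition", and number 11 as "Abnormal lab or ECG at screen".

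Section 5d describes a "baseline visit when they will receive the study medication", and Section 5f starts titration at "baseline (week 0) 5 mg/day BID". Section 5f also lists "Vital signs including blood pressure (standing/supine") among the measures taken at all visits, with a further check within 8 hours of the first dose.

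Section 6 holds the only numerical limits for low pressure. The absolute limit covers a patient who "develops clinically significant hypotension (e.g., systolic blood pressure equal to or less than 90 mm Hg or diastolic equal to or less than 60" (both in mm Hg), or who has significant associated symptoms. The relative limit is a fall of 20% or more from baseline at any time after baseline. Either one leads to stopping the study medication and leaving the protocol.

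**The concern.** The protocol gives 90 systolic or 60 diastolic as an example of clinically significant hypotension and as a reason to stop isradipine, yet a patient at that level before dosing meets no exclusion. The rule in Section 6 describes hypotension that develops, and its action is to discontinue the drug. It governs what happens on treatment and does not screen the pressure a patient brings to the trial.

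At stake is avoidable exposure. Section 2 describes calcium-channel blockers as widely used antihypertensives, and Section 5f bases the dose partly on the labelling for hypertension. Exclusions 6 and 7 remove treated and uncontrolled hypertension, so the drug goes largely to people with no blood-pressure reason to take it. Section 6 lists hypotension first among the common side effects and names syncope and severe hypotension among the rare ones. Section 8 says there may be no immediate benefit to the subject.

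**Working it through.** This is a check of the text, with a small amount of arithmetic on the stopping limits. The plan states no figure to reproduce.

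**1. Count of criteria (Section 5b).** 7 numbered inclusion + 12 numbered exclusion = 19. The exclusion numbering runs from 1 to 12 without a gap or redaction.

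| Criterion | Subject | Sets a lower pressure limit? |
|---|---|---|
| Exclusion 5 | Unstable medical problem affecting cognition | No |
| Exclusion 6 | Treated hypertension | No |
| Exclusion 7 | Uncontrolled hypertension | No |
| Exclusion 8 | History of heart disease | No |
| Exclusion 9 | Drugs interacting with isradipine | No |
| Exclusion 11 | Laboratory tests and ECG, not vital signs | No |
| The other 13 | Unrelated to blood pressure | No |

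Criteria concerning blood pressure: 2. Criteria with a lower limit: 0 of 19. The unnumbered restrictions (antipsychotic count and ECT in Section 5b, vulnerable groups in Section 14) do not mention blood pressure.

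**2. Readings available before the first dose.** Section 5f measures pressure at all visits, so two visits supply a reading: screening and baseline. No section says what to do if either is low.

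**3. When the other safeguards act.** The check within 8 hours (Sections 5f and 5i) follows the first dose. The contact number (Section 5i) is handed over before the dose but serves problems that arise after it. Discontinuation for clinical worsening (Section 5j) applies to a patient already in the trial. None prevents the first dose.

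**4. What Section 6 does for a patient entering at 90 systolic or 60 diastolic.**

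- *If the absolute limit is read as needing hypotension to develop*, a patient who arrived with it has arguably not developed it. The only numerical limit that then clearly applies is the relative one: 90 × (1 − 0.20) = 72 mm Hg systolic, or 60 × (1 − 0.20) = 48 mm Hg diastolic. Symptoms or the physician's judgement could stop the drug sooner.
- *If the absolute limit is read as a plain on-treatment ceiling on risk*, the patient is dosed and then meets the stopping value at the first post-dose check unless pressure has risen. Section 5f gives the MCCB only at baseline and week 4, and Section 5h says a subject missing a complete cognitive visit cannot be meaningfully analysed. Such a patient takes the risk and is unlikely to contribute to the primary endpoint.

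For comparison, a 20% fall reaches the absolute limits from 90 / 0.80 = 112.5 mm Hg systolic and 60 / 0.80 = 75 mm Hg diastolic. Below those starting values the absolute limit is the stricter of the two. The patients for whom it matters most are therefore those who enter with lower pressures.

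**The case against.** The strongest reply is textual. In Section 6 only the 20% limit is expressly confined to the period after baseline. The absolute limit carries no such restriction, follows directly on a statement that pressure is measured at every visit, and leads to exclusion from the protocol as well as to stopping the drug. It could be read as covering the baseline reading. This shows some ambiguity. It does not displace the natural reading, because developing hypotension and being discontinued from a medication both presuppose exposure. If the sponsor did intend the wider reading, the eligibility list is where staff would need to find it.

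Second, exposure may be brief. Dosing is twice daily and pressure is checked within 8 hours, so under the absolute limit the gap may amount to roughly the first dose. Exclusions 8 and 9 remove patients with heart disease or interacting drugs, exclusion 6 removes those on antihypertensive treatment, and a physician may decline to dose. These points stand as mitigation, but none obliges anyone to withhold the dose.

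Third, the values are given as examples, and a habitual, symptom-free diastolic of 60 need not mean the same as a drug-induced fall to 60. An entry limit at those values still admits a patient at 91/61, and the protocol does not say whether the standing or the supine reading governs. These are fair points about how to word the criterion, and they do not argue for having none.

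Finally, the document was revised in May 2017 and Section 5d anticipates completion in July 2017, so few enrolments may remain. That limits the practical yield of an amendment but not the validity of the point.

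**Conclusion.** The concern holds. None of the 19 numbered criteria sets a lower blood-pressure limit, and neither of the two pre-dose readings has an action attached. A patient at the protocol's own example of clinically significant hypotension can be given isradipine. This is a gap that should be closed. It does not show that any patient has been or will be harmed.

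The conclusion rests on reading the absolute limit in Section 6 as an on-treatment rule, which its wording favours but does not put beyond doubt; confidence is medium for that reason. How many patients would be affected is unknown, because the documents report no baseline pressures.

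**What to change.** Add one exclusion to Section 5b: systolic pressure at or below 90 mm Hg or diastolic at or below 60 mm Hg at screening or at the pre-dose baseline reading. State whether the standing or supine reading governs, and say that the baseline reading must be reviewed before the first dose is released. Patients just above the limit would still enter and remain covered by the Section 6 stopping rule and the 8-hour check. A higher limit would give more margin, but the protocol's own values are the minimum for consistency.

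The cost is one line of text and no new measurement or visit. Some otherwise eligible patients would not be enrolled, in a number the documents do not allow to be estimated. Little information would be lost: under the absolute limit those patients would be stopped at the first post-dose check unless their pressure had risen, and so would be unlikely to reach the week 4 cognitive assessment.

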Data from this study may be used in medical publications or presentations. The information will be de-identified so that individual subjects cannot be recognized and the information will no longer be considered PHI. The information that is collected for research will be analyzed for many years and it is not possible to know how long this analysis and follow-up will take. Therefore, participants are allowing access to this information indefinitely.

Subjects will only be identified with a numerical code in compliance with HIPAA regulations. Raw subject data will be secured in double locked physical control. Digitized raw data will be similarly de-identified using coding and will be secured on an MS SQL server with Windows integrated security.

	Protocol Title:	A Molecular Approach to Treat Cognition in Schizophrenia: Ca 2+ Channel Blockade
	Principal Investigator Name/Contact Info:	[name] [contact]
	Primary Contact Name/Contact Info	[name] [REDACTED]
	Date Revised:	May 16, 2017
	Study Number:	HSM# 12-0031, GCO# 12-0679, GCO# 13-1987

Data analysis plan is included below. All analyses will be based on an intent-to-treat sample of subjects who received at least one dose of isradipine. Since the missing values may be dependent on the observed outcomes, we assume the missing data mechanism to be missing at random, and hence a mixed models analysis will be used to assess the treatment effect of isradipine with fixed effects for week and first order autoregressive covariance structure to evaluate change over time for all of the primary outcome measures. Cognitive measures will be handled differently, as these will only be collected at two time points – if missing data are substantial (or a complete visit is missing), subjects' data will not/cannot be meaningfully analyzed.

*Primary Analyses* will test the following hypotheses based on our specific aims:

To determine the feasibility of 4 weeks of isradipine on cognitive outcomes in SZ.  
Hypothesis: We will successfully recruit up to 80 stable schizophrenia and schizoaffective patients

To determine the safety of 4 weeks of isradipine on cognitive outcomes in SZ.  
Hypothesis: The frequency of new or worsened side effects (clinician-rated; self-reported; lab-based) will not be significantly different from baseline to end of study visit.

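### The MCCB result will describe only patients who reach a week-4 MCCB, in effect completers, although the plan says all its analyses are intent-to-treat

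*Combined protocol and SAP*

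**What the plan says.** Section 5e makes the MCCB the primary efficacy endpoint, and section 5f schedules it at baseline and week 4 only.

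Section 5h sets the analysis population: "All analyses will be based on an intent-to-treat sample of subjects who received at least one dose of isradipine". It then plans a mixed model under a missing-at-random assumption, but takes cognition out of it: "Cognitive measures will be handled differently, as these will only be collected at two time points". The exclusion follows in the same sentence: "if missing data are substantial (or a complete visit is missing", the plan says, that patient's data will not or cannot be usefully analysed. No other name is given to the MCCB population, and no sensitivity analysis or count of exclusions is planned.

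The stopping rules are spread over three sections:

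- Section 5f, intolerance: "If 5 mg cannot be tolerated, the subject will be discontinued".
- Section 5j: a 2-point CGI worsening, risk of suicidal behaviour, other clinical worsening, and SAEs ("any instance of an SAE will be discontinued"). Patients unable to follow the protocol are both discontinued and withdrawn.
- Section 6, symptoms: clear worsening ends participation.
- Section 6, blood pressure: clinically significant hypotension, or if "there is a blood pressure drop of 20% or more from blood pressure at baseline". In either case "they will be discontinued from the study medication and excluded from the protocol".

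For a patient who stops, section 5j plans the following: "Safety measures would be collected and a follow-up visit by phone would be scheduled to further ensure safe discontinuation". An in-person visit comes afterwards only if needed to deal with remaining concerns. No MCCB is listed.

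**The concern.** The plan gives its primary efficacy endpoint a property that the endpoint will not have. An intent-to-treat claim tells the reader that the result speaks for everyone who took a first dose. By the plan's own rules, a patient stopped before week 4 has no second MCCB and drops out of the result.

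The stops are not incidental. Hypotension is listed in section 6 as a common effect of isradipine, and intolerance, SAEs and symptom worsening may also be related to treatment. The trial has one arm, so imbalance between groups is not the problem. The problem is that the pre-post change, which is the whole efficacy result, is measured in a group partly selected by how patients fared on the drug. Section 8 says the results may support larger pivotal trials, so it matters which population they describe.

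**Working it through.** **Does the conclusion follow from the text?**

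1. An MCCB change needs both scheduled assessments, baseline and week 4 (section 5f).
2. Section 5d has patients receive the drug at the baseline visit, and section 5f schedules a baseline MCCB then. Dosed patients should therefore have the first assessment; the second is the one that is lost.
3. Five blood-pressure checks come before week 4: 8 hours after the first dose, week 1, week 2, 8 hours after the dose increase, and week 3. The other stopping rules can also act at any time before week 4.
4. A patient stopped at any of these points has no planned MCCB (section 5j). Under several rules the patient has also left the study (sections 5j and 6).
5. A patient with a missing cognitive visit is not analysed (section 5h).

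Together, these steps make the MCCB set the dosed patients with both MCCB visits. That equals the intent-to-treat set only if nobody stops early. A patient who first meets a rule at week 4 may still have an MCCB and is outside this point.

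**How large could the effect be?** The plan gives no dropout rate, SD, effect size or power, so there is no figure to reproduce. What follows is illustration.

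Let d be the share of dosed patients without a week-4 MCCB, K the mean change in those kept and S the mean change in those stopped.

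- All-dosed mean = (1 − d)·K + d·S
- Completers mean minus all-dosed mean = K − [(1 − d)·K + d·S] = d·(K − S)

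With 80 patients (the recruitment ceiling), assumed d of 10% to 40%, and an assumed |K − S| of 0.25 or 0.5 SD:

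| d | Stopped, 80·d | With week-4 MCCB | Shift at 0.25 SD | Shift at 0.5 SD |
|---|---|---|---|---|
| 10% | 8 | 72 | 0.025 SD | 0.05 SD |
| 20% | 16 | 64 | 0.05 SD | 0.10 SD |
| 30% | 24 | 56 | 0.075 SD | 0.15 SD |
| 40% | 32 | 48 | 0.10 SD | 0.20 SD |

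The sign of K − S is unknown, so the shift could go either way.

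**Can d be narrowed from the blood-pressure rule?** No. The 20% clause alone was simulated over the five checks, with 200,000 patients per setting. Every input was assumed: mean 120/76 mm Hg, between-person SD 10/7, within-person SD 7/5 to 10/7, one baseline reading, and noise correlations of 0.6 between postures and 0.5 between systolic and diastolic. With no drug effect the clause fired in 2.0% to 37.1%, depending on the noise and on which readings count. With an assumed uniform fall of 5/3 mm Hg it fired in 7.7% to 56.8%. Ranges this wide show only that the documents do not fix the stop rate. They are not forecasts.

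**What would testing stopped patients do?** If every stopped patient attended at week 4 off drug and no drug effect persisted, the drug part of the all-dosed mean would be multiplied by 1 − d. For d of 10% to 40% that is 0.90 to 0.60.

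**The case against.** The strongest reply is that section 5h discloses the handling. Soon after the general statement it says cognition is treated differently and that a patient missing a visit is not analysed. The specific rule qualifies the general one. This stands in part: a careful reader is told, and nothing is concealed. What remains is a general claim that is untrue for the primary efficacy endpoint, with no name for the population actually used and no account of who is left out.

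A second reply is that on-drug change in patients who tolerate four weeks is a defensible target for a short, open-label, single-arm trial. That also stands. The point concerns what the result is called and to whom it applies, and does not require a different primary analysis.

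A third is that testing stopped patients would not reveal selection. Those kept would be tested on drug and those stopped off drug, and without a control arm a difference between them could be selection or loss of exposure. This is correct, and it is why such data can only be supportive.

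A reader might go further and infer that the MCCB result will be inflated because stopped patients do worse. The documents do not support that: they give no stop rate and link neither blood-pressure response nor any other stopping reason to MCCB change. A reader might also infer that the blood-pressure rule is the fault. It is a safety rule, and other rules in sections 5j and 6 end participation too.

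**Conclusion.** The point holds as a mismatch between the stated and the actual population for the primary efficacy endpoint. That conclusion rests on the text alone and needs no assumed figure. As planned, the MCCB result is a completers result and supports conclusions only about patients with both MCCB visits.

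The numerical consequence is unknown. The 0.025 to 0.20 SD shifts depend entirely on an assumed 10% to 40% loss and an assumed 0.25 to 0.5 SD difference, and their direction is open. They show that the effect could be negligible or material; they do not show that bias is present. The correction is worth making because it is almost free and puts the right limit on the efficacy conclusion.

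**What to change.** **Main change, section 5h:**

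- Limit the intent-to-treat statement to the outcomes analysed by mixed model over repeated visits and to the safety outcomes.
- Name the MCCB set as dosed patients with both MCCB visits, and call them completers.
- Restrict the efficacy conclusion to that set.
- Report how many dosed patients are excluded, by reason: blood pressure, 5 mg intolerance, SAE, CGI or other clinical worsening, suicide risk, inability to follow the protocol, and own withdrawal.
- Compare baseline MCCB between patients kept and patients stopped. This describes who was lost; it cannot show whether their change would have differed.

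This needs only a text change and data the trial already collects, and it applies to every patient.

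**Low-cost addition, for patients not yet past week 4:** in section 5j and in both the symptom-worsening and blood-pressure rules of section 6, separate stopping the drug from ending participation. Invite stopped patients, where willing and safe, to the scheduled week-4 MCCB. All three places need editing, or the invitation would contradict wording left in force. Report the combined on- and off-drug data only as a supportive sensitivity analysis, because of the dilution and the mixing of selection with lost exposure. Safety thresholds stay as they are.

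The addition costs a protocol and consent amendment plus one test session per stopped patient who accepts. That is at most 8 to 32 sessions in 80 patients at the assumed 10% to 40% loss, or about 45 at the highest simulated rate (0.568 × 80 = 45.4). The real number would be smaller: some patients will decline, and the text is dated May 16, 2017 with an anticipated final date of 7/2017, so few patients may still be before week 4.
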